**8.3.4. Regulatory Reporting Requirements for SAEs**

- Prompt notification by the investigator to the sponsor of an SAE is essential so that legal obligations and ethical responsibilities towards the safety of participants and the safety of a study intervention under clinical investigation are met.
- The sponsor has a legal responsibility to notify both the local regulatory authority and other regulatory agencies about the safety of a study intervention under clinical investigation. The sponsor will comply with country-specific regulatory requirements relating to safety reporting to the regulatory authority, Institutional Review Boards (IRBs)/Independent Ethics Committees (IECs), and investigators.
- For SAEs, the investigator must always provide an assessment of causality at the time of the initial report, as defined in Section 10.3.4 [Updating of SAE and pregnancy information after removal of write access to the participant's eCRF](#).
- An investigator who receives an investigator safety report describing an SAE or other specific safety information (e.g., summary or listing of SAEs) from the sponsor will review and then file it along with the IB/ package insert and will notify the IRB/IEC, if appropriate according to local requirements.
- Investigator safety reports must be prepared for suspected unexpected serious adverse reactions (SUSARs) according to local regulatory requirements and sponsor policy and forwarded to investigators as necessary.

**Table 2 Timeframes for submitting SAE and pregnancy reports to GSK**

Type of event	Initial reports	Follow-up of relevant information on a previous report		
	Timeframe	Documents	Timeframe	Documents
SAEs	24 hours*†	Paper/electronic AEs report	24 hours*	Paper/electronic AEs report
Pregnancies	24 hours*	Paper pregnancy notification report/electronic pregnancy report	24 hours*	Paper pregnancy follow-up report/electronic pregnancy report

Type of event	Initial reports	Follow-up of relevant information on a previous report		
	Timeframe	Documents	Timeframe	Documents

AE = Adverse event; CRF/eCRF = Case report form/electronic case report form; SAE = Serious adverse event.

\* Timeframe allowed after receipt or awareness of the information by the investigator/site staff.

† Paper AEs Report will be dated and signed by the investigator (or designee). For each SAE, the investigator(s) must document in the medical notes that they have reviewed the SAE and have provided an assessment of causality.

### 8.3.5. Pregnancy

- Details of all pregnancies in female participants will be collected after the start of study intervention and until at least 3 days after the last dose of study intervention.
- If a pregnancy is reported, the investigator will record pregnancy information on the appropriate form and submit it to GSK within 2 weeks of learning of the female participant pregnancy. While pregnancy itself is not considered to be an AE or SAE, any pregnancy complication or elective termination of a pregnancy for medical reasons will be reported as an AE or SAE.
- Abnormal pregnancy outcomes (e.g., spontaneous abortion, fetal death, stillbirth, congenital anomalies, ectopic pregnancy) are considered SAEs and will be reported as such.
- The participant will be followed to determine the outcome of the pregnancy. The investigator will collect follow-up information on the participant and the neonate and the information will be forwarded to the sponsor.
- Any post-study pregnancy-related SAE considered reasonably related to the study intervention by the investigator will be reported to the sponsor as described in Section 8.3.4. While the investigator is not obligated to actively seek this information in former study participants, he or she may learn of an SAE through spontaneous reporting.
- Any female participant who becomes pregnant while participating in the study will discontinue study intervention.

### 8.3.6. Cardiovascular and Death Events

For any cardiovascular events detailed in Section 10.3.3. and all deaths, whether or not they are considered SAEs, specific Cardiovascular (CV) and Death sections of the CRF will be required to be completed. These sections include questions regarding cardiovascular (including sudden cardiac death) and non-cardiovascular death.

The CV CRFs are presented as queries in response to reporting of certain CV Medical Dictionary for Regulatory Activities (MedDRA) terms. The CV information should be recorded in the specific cardiovascular section of the CRF within one week of receipt of a CV Event data query prompting its completion.

The Death CRF is provided immediately after the occurrence or outcome of death is reported. Initial and follow-up reports regarding death must be completed within one week of when the death is reported.

### 8.3.8. Adverse Events of Special Interest

There are no adverse events of special interest in this study.

### 8.3.9. Participant card

The investigator (or designee) must provide the participant with a “participant card” containing information about the clinical study. The participant must be instructed to always keep the participant card in their possession for the duration of the study. In an emergency, this card serves to inform the responsible attending physician/caregiver/family member that the participant is in a clinical study and that relevant information may be obtained by contacting the investigator(s) or their back up

## 8.4. Pharmacokinetics

### PK Urine Sample Collection

[figure not shown]
- Urine samples will be collected as specified in the SoA. The time will be recorded for each urine sample collected, and the total urine volume for each participant will be recorded over the collection time period.
- From each urine PK interval, a 1 mL aliquot of urine will be collected for PK analysis and stored at approximately 70°C or colder.

### PK Plasma Sample Collection

- Whole blood samples of approximately 1 mL will be collected for measurement of plasma concentrations as specified in the SoA.

- Samples will be used to evaluate the PK of GSK3882347. Samples collected for analyses of study intervention plasma concentration may also be used to evaluate safety or efficacy aspects related to concerns arising during or after the study. Residual PK Plasma samples may be analyzed for other compound-related metabolites and the results reported under a separate in vivo/in vitro (IV/IVT), GSK protocols.
- Drug concentration information that would unblind the study will not be reported to investigative sites or blinded personnel until the study has been unblinded.

#### **8.4.1. Pharmacodynamics**

#### **8.5. Genetics**

A 6 mL blood sample for DNA isolation will be collected from participants who have consented to participate in the genetics analysis component of the study. Participation is optional. Participants who do not wish to participate in the germline (host) genetic research may still participate in the study.

In the event of DNA extraction failure, a replacement genetic blood sample may be requested from the participant. Signed informed consent will be required to obtain a replacement sample unless it was included in the original consent.

See Section 10.5. Genetics and Pharmacogenomics for information regarding genetic research. Details on processes for collection and shipment and destruction of these samples can be found in the SRM.

#### **8.6. Biomarkers**

Biomarkers are not evaluated in this study.

#### **8.7. Immunogenicity Assessments**

Immunogenicity assessments are not conducted in this study.

#### **8.8. Health Economics**

Health economic parameters are not evaluated in this study.

## **8.9. Administrative and general/baseline procedures**

### **8.9.1. Collection of demographic data**

Record demographic data such as year of birth, sex, race, and ethnicity in the participant's eCRF.

Collection of sex, race and ethnicity data is necessary to assess and monitor the diversity of the trial participants, and to determine if the trial participants are truly representative of the impacted population.

### **8.9.2. Medical history**

Obtain the participant's medical history by interviewing the participant/LAR(s) and/or review of the participant's medical records. Record any pre-existing conditions, signs and/or symptoms present prior to the first dose of study intervention in the eCRF.

## **9. STATISTICAL CONSIDERATIONS**

The SAP will include a more technical and detailed description of the statistical analyses described in this section. This section is a summary of the planned statistical analyses of the most important endpoints including primary and key secondary endpoints.

### **9.1. Statistical Hypotheses**

No formal statistical hypotheses will be tested in this study.

### **9.2. Analysis Sets**

For purposes of analysis, the following populations are defined.

Population	Description
Randomized Population	All participants randomly assigned to study intervention.
Safety Population	All randomized participants who receive at least 1 dose of study intervention. Participants will be analyzed according to their actual intervention received.
PK Population (Sub populations identified for Cohort 1 and Cohort 2)	All randomized participants who have a valid PK sample taken and from whom a measurable plasma or urine concentration, even if the concentration below assay's limit of quantification, (for the actual study intervention) received.  Separate Sub populations will be constructed for participants Randomised to Cohort 1 and Cohort 2 who were in the PK population. [Note: these sub-populations support analyses

Population	Description
	involving PK parameters that can only be derived from a full intensive PK time profile].
Microbiological Modified Per Protocol (Micro-MPP) Population*	All participants randomly assigned to study intervention who receive all planned doses of study intervention and have a Qualifying baseline E. coli from a quantitative bacteriological culture of a pre-treatment clean-catch midstream urine specimen.

\*The algorithm for determining qualifying *E. coli* based on microbiology laboratory quantitative culture results is provided in the Section 10.8.

Details of additional populations, including targeting non-*E. coli* will be provided in the SAP.

### 9.3. Statistical Analyses

#### 9.3.1. General Considerations

The estimands for primary endpoint, Microbiological response rate and secondary endpoints safety and PK are included in Section 3. No formal comparisons against Nitrofurantoin are planned as Nitrofurantoin is included in the study only to ensure unbiased reporting of safety events and analysis was designed to demonstrate that the concept behind the novel mechanism of action of GSK3882347 translates into humans. Clinical outcomes, response rates, CCI form part of the exploratory analysis. Additional exploratory analysis may be conducted on the microbiology samples according to other uropathogen in combination with the qualifying pathogen and CCI to understand the microbiology response rate further depending on the main study results.

In general, data from Cohorts 1 and 2 will be displayed in a single (combined) Table/Figure/Listing; except for selected PK analyses which can only be performed with the full serial time profile.

Microbiological response is the key endpoint used for internal decision-making and additional supportive analyses for internal decision-making may focus on the clinical resolution at the ToC visit, and CCI at ToC and Follow Up visit. CCI

#### 9.3.2. Primary Endpoint(s)/Estimands(s) Analysis

The analysis of primary endpoint will be done using the Micro-MPP population. The primary endpoint to be estimated is microbiological response at ToC visit in female participants with a qualifying baseline *E.coli*.

Microbiological response at the ToC visit is defined as;

- **Microbiological Success:** Reduction in *E. coli* count to  $<10^3$  CFU/mL (no growth) for any *E. coli* identified at ToC visit, without receiving other systemic antimicrobials (rescue medications) prior to ToC.
  - If the baseline urine microbiology quantitative culture has  $>1$  *E. coli* strain present at  $\geq 10^4$  CFU/mL, both *E. coli* strains must have a reduction to  $<10^3$  CFU/mL (no growth) to achieve microbiological success.
- **Microbiological Failure:** All other microbiological outcomes (for example but not limited to  $\geq 10^3$  CFU/mL for any *E. coli* identified at ToC visit), use of rescue medication prior to ToC, lost to follow-up before ToC, missing/unevaluable samples at ToC, etc).

Use of rescue medications before ToC is captured through the definitions of microbiological response and will be counted as a failures (Composite strategy). Participants who are lost to follow-up prior to ToC, have a missing/unevaluable sample at ToC, discontinue treatment due to any reasons prior to ToC (withdrawal of consent/AEs/missed doses) will be excluded from the analysis and the participant may be replaced at the discretion of the Sponsor. The number and percentage of participants with each category of microbiological response at ToC visit will be summarized, along with 95% CI.

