### 1.1.1. Estimand for Primary Endpoint

The primary clinical question of interest is: *What is the microbiological response for GSK3882347 assessed at ToC in participants with acute uUTI caused by E. coli at Baseline who completed the planned course of treatment (5 days) and had no major deviations from protocol that would prevent evaluation of microbiological response (as defined in the protocol deviation rules document). Use of rescue medication after last dose of study intervention will be set to non-responder in the endpoint definition.*

The Primary estimand is described by the following attributes:

- Population: Female participants with acute uUTI with a qualifying baseline *E. coli* (Section 6.4) at baseline who completed the planned course of treatment (5 days) and had no major deviations from protocol that would prevent evaluation of microbiological response
- Treatment condition: GSK3882347 CCI mg given orally CCI for 5 days or Nitrofurantoin 100mg given orally twice daily for 5 days.
- Variable: Microbiological response at ToC visit (see Section 4.2.1)
- Summary measure: Frequency and percentage of participants with microbiological response (responder/non-responder) in GSK3882347 treatment group
- Main intercurrent events anticipated:

- Use of rescue medication prior to ToC visit- Composite strategy
- This intercurrent event is captured through the definitions of microbiological response (see Section 4.2.1). Hence the participants who take rescue medication prior to ToC visit will be considered as non-responders.
- Participants who are lost to follow-up prior to ToC, have a missing/ unevaluable sample at ToC, discontinue study treatment due to any reason (withdrawal of consent/AEs/missed doses) will not be included in the analysis and may be replaced at the discretion of the Sponsor.
- Rationale for estimand:

Use of rescue medication may impact microbiological outcomes and its use implies that the treatment the participant received is not working, therefore, the definition of a successful microbiological response precludes the use of rescue medications. In this small, early phase, proof of mechanism study, interest lies in the treatment effect of participants who completed the planned course of treatment and follow important components of the study protocol to establish proof of mechanism.

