### 3. ANALYSIS SETS

Analysis Set	Definition / Criteria	Analyses Evaluated
Screened	All participants who signed the ICF and were screened for eligibility.	
 
Study Population
 

Enrolled	
All participants who passed screening and entered the study
 
Note: screening failures [who never passed screening even if rescreened] and participants screened but never enrolled into the study [Met eligibility but not needed] are excluded from the Enrolled analysis set as they did not enter the study.)
	
 
Study Population
 

Randomized	
All participants in the Enrolled analysis set who were randomly assigned to study intervention in the study.
 
Participants will be analyzed according to the intervention they were randomly assigned to.
	
 
Study Population
 

Safety	
All participants in the Randomized analysis set who receive at least 1 dose of study intervention.
 
Participants will be analyzed according to their actual intervention received.
	
 
Safety
 

Microbiological Modified Per Protocol (Micro-MPP)*	
All participants in the Safety analysis set who: receive all planned doses of study intervention; have a Qualifying baseline E. coli from a quantitative bacteriological culture of a pre-treatment clean-catch midstream urine specimen; have completed a ToC visit; have no major protocol deviations that would prevent evaluation of microbiological response.
 
Participants will be analyzed according to their actual intervention received.
	
 
Efficacy
 

CCI

CCI

Analysis Set	Definition / Criteria	Analyses Evaluated
CCI		
Pharmacokinetic (PK)	
All participants in the Safety analysis set who had at least 1 non-missing PK assessment (Non-quantifiable [NQ] values will be considered as non-missing values).
 
Participants will be analyzed according to their actual intervention received.
	
 
Pharmacokinetic
 

CCI		

\*The algorithm for determining qualifying *E. coli* based on microbiology laboratory quantitative culture results is provided in the [Appendix 4](#)

CCI

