**Table 2 Changes to Protocol Defined Analysis Plan**

SAP version	Protocol Defined Analysis	SAP Defined Analysis	Rationale for Changes
Original	
 
 Microbiological Success:  Microbiological response of <math><10^3</math> CFU/mL for all qualifying E. coli identified at Baseline in urine microbiology count at ToC visit, without receiving other systemic antimicrobials (rescue medications) prior to ToC.   If the Baseline urine microbiology count has <math>>1</math> E. coli strain present at <math>>10^4</math> CFU/mL, both strains must have a response of <math><10^3</math> CFU/mL to achieve microbiological success. 
 
 Microbiological Failure: All other outcomes (for example but not limited to <math>\geq 10^3</math> CFU/mL for any qualifying E. coli identified at Baseline, use of rescue medication prior to ToC, lost to follow-ups before ToC, missing/unevaluable samples at ToC, etc). 
 
	
 
 Microbiological Success:  Microbiological response of <math><10^3</math> CFU/mL for any E. coli (qualifying or non-qualifying at baseline) at test-of-cure.   Any participant in the Micro-MPP population with E. coli <math><10^3</math> CFU/mL (no E. coli) at TOC. 
 
 Microbiological Failure: All other outcomes (for example, but not limited to, <math>\geq 10^3</math> CFU/mL for any E. coli (qualifying or non-qualifying at baseline), use of rescue medication prior to ToC, lost to follow-ups before ToC, missing/unevaluable samples at ToC).   Any participants in the Micro-MPP population with E. coli <math>\geq 10^3</math> CFU/mL at TOC. 
 
	
 
Clarification to microbiological success/failure criteria based on FDA comment
 

Amendment 1	
 
Protocol amendment 4 updated definition of micro-ITT to require "all planned doses" rather than "at least 1 dose" and rename as Micro-MPP.
 
	
 
Definition of Micro-MITT and CCI: All eligible participants randomly assigned to study intervention who receive at least one dose of study intervention and have a Qualifying baseline E.coli (Micro) CCI
 
	
 
CCI
 

SAP version	Protocol Defined Analysis	SAP Defined Analysis	Rationale for Changes

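### Participants lost before ToC or without an evaluable ToC culture are both counted as failures and excluded, so the primary denominator rests on two conflicting rules

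*Protocol*

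**What the plan says.** **Failure.** Protocol 9.3.2 defines microbiological failure as every outcome other than success. Its examples include "lost to follow-up before ToC, missing/unevaluable samples at ToC, etc". SAP Table 2 (section 4.8), in the column for the SAP-defined analysis, keeps the same two categories in its failure definition: "lost to follow-ups before ToC, missing/unevaluable samples at ToC".

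**Exclusion.** The paragraph after the failure bullet in Protocol 9.3.2 covers "Participants who are lost to follow-up prior to ToC, have a missing/unevaluable sample at ToC, discontinue treatment due to any reasons prior to ToC" and says that they "will be excluded from the analysis and the participant may be replaced at the discretion of the Sponsor". The primary estimand in Protocol 3 takes the same line. SAP 1.1.1 says that such participants "will not be included in the analysis and may be replaced at the discretion of the Sponsor".

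**Analysis set.** Protocol 9.2 defines Micro-MPP as "All participants randomly assigned to study intervention who receive all planned doses of study intervention and have a Qualifying baseline" *E. coli*, with no ToC requirement. SAP section 3 adds two conditions: participants must "have completed a ToC visit; have no major protocol deviations that would prevent evaluation of microbiological response".

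**Rescue.** SAP 1.1.1 makes rescue before ToC a non-response by a composite strategy. It specifies that for this population rescue means use after the last dose. Protocol 6.8.3 sends anyone given antibiotic rescue to an early discontinuation visit and requires no visits after it. Protocol 7.1 says the same where the need for rescue ends study treatment.

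**The concern.** One rule keeps a participant in the denominator as a non-responder. The other takes her out and may replace her. A program can apply only one of them to a given participant, and the two give different primary response rates.

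The plan tests no hypothesis (Protocol 9.1), so no error rate is at stake. What is at stake is the estimate itself. Protocol 9.3.1 names microbiological response as the key endpoint for the sponsor's internal decisions, and it is estimated from only about 21 participants on GSK3882347. At that size each reclassified participant moves the rate visibly.

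There is a second, smaller problem. If entry to Micro-MPP depends on a ToC visit, a woman who finishes dosing, is then rescued and skips ToC, as the protocol allows, may never enter the set in which she is meant to count as a failure.

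**Working it through.** **1. Which rule applies to whom**

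| Participant (all doses taken, qualifying baseline *E. coli*) | Failure definition (Protocol 9.3.2, SAP Table 2) | Exclusion text (Protocol 3, 9.3.2; SAP 1.1.1) | In Protocol Micro-MPP? | In SAP Micro-MPP? |
|---|---|---|---|---|
| Lost before ToC | Failure | Excluded | Yes | No (no ToC visit) |
| Attends ToC, culture missing or unevaluable | Failure | Excluded | Yes | Yes, unless classed as a major deviation |
| Rescued after last dose, no ToC visit | Failure | Not excluded on account of rescue; counted as non-responder | Yes | No, read literally |

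The first row is a conflict in the protocol that the SAP set largely resolves. The second remains open in the visible SAP text. SAP 4.4.6 plans an indeterminate culture category by visit within Micro-MPP, which is consistent with such participants being in the set. In the third row the set definition works against the composite strategy.

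**2. Inputs for the size**

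- About 21 evaluable participants on GSK3882347, the recruitment stopping count (Protocol 1.1).
- 95% Clopper-Pearson interval (SAP 4.2.2).
- Number of successes x and number without a ToC result m: the documents give neither, so both are assumptions.

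The plan has no figure of its own for this point. Its randomization maxima of 122 and 141 cannot be reproduced, because the visible text does not give the evaluability rate. At 3:1 allocation they imply 21/(122 × 0.75) = 21/91.5 = 23.0% and 21/(141 × 0.75) = 21/105.75 = 19.9%. Neither maximum depends on which rule is chosen.

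**3. Formula**

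Take 21 participants with a ToC result and m further participants without one. Exclusion gives x/21 and failure gives x/(21 + m). The gap is x/21 − x/(21 + m) = x·m / [21(21 + m)].

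**4. Results**

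| x | m | Exclusion | Failure | Gap (points) |
|---|---|---|---|---|
| 7 | 1 | 7/21 = 33.3% (14.6-57.0) | 7/22 = 31.8% (13.9-54.9) | 1.5 |
| 12 | 3 | 12/21 = 57.1% (34.0-78.2) | 12/24 = 50.0% (29.1-70.9) | 7.1 |
| 14 | 3 | 14/21 = 66.7% (43.0-85.4) | 14/24 = 58.3% (36.6-77.9) | 8.3 |
| 17 | 1 | 17/21 = 81.0% (58.1-94.6) | 17/22 = 77.3% (54.6-92.2) | 3.7 |
| 17 | 5 | 17/21 = 81.0% (58.1-94.6) | 17/26 = 65.4% (44.3-82.8) | 15.6 |

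Over m = 1 to 5 and x = 7 to 17 the gap runs from 1.5 to 15.6 points. For a single missing result it is x/462, so it grows with the number of successes.

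**5. The stopping count**

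Protocol 1.1 counts participants who complete a ToC visit, not those with an evaluable culture. If m of the 21 counted have no usable culture and are not replaced, exclusion leaves 21 − m. With x = 12 and m = 3 that is 12/18 = 66.7%, against 12/21 = 57.1% under failure.

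**The case against.** The strongest reply is that exclusion is the dominant reading. It appears in both estimand sections and in the second paragraph of Protocol 9.3.2, and it fits the stated interest in participants who completed treatment and followed the protocol. The SAP set already removes those lost before ToC. Its major-deviation clause may also remove a participant with an unusable culture, and the deviation rules document is not available to show this. SAP 4.2.1 assigns response by a prespecified algorithm, and the ToC part of Appendix 6 that would show it is not visible. Table 2 is a table of changes, and the row in question is labelled as belonging to the original SAP.

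Much of this stands. It limits the open SAP case to the unevaluable culture and makes that case conditional. It does not remove the contradiction inside Protocol 9.3.2. Nor is the Table 2 row simply old text: it uses the name Micro-MPP, which Protocol Amendment 4 introduced, so the row was edited later and the failure wording was kept.

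A reader might infer three stronger things that the documents do not support:

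- **That the rule could be chosen after results are seen.** SAP 4.2.1 points to a prespecified algorithm, and SAP 6.1.3 has deviations that lead to exclusion reviewed before unblinding and database freeze.
- **That failure is the only acceptable rule.** It is the SAP's convention for non-attendance in the clinical resolution endpoint (4.4.3), but imposing it here would override a stated and reasoned completer estimand.
- **That uncured participants are likelier to be lost, so exclusion flatters the drug.** This is possible, but nothing in the documents bears on it.

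**Conclusion.** The concern holds as a contradiction that must be reconciled. Two stated rules give different primary denominators. The conflict is complete within Protocol 9.3.2. In the visible SAP text it narrows to participants who attend ToC without an evaluable culture, unless the deviation rules or Appendix 6 settle their status. Separately, the SAP's ToC-visit condition, read literally, can remove rescued participants whom the estimand counts as non-responders.

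The size is illustrative only, because the success count and the number missing are both assumed. At 12 successes and 3 missing the rate is 57% or 50%, and the intervals overlap heavily. The decision criteria are not visible, so it cannot be shown that a shift of this size would change a decision.

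**What to change.** Before unblinding, choose one rule and state it identically in Protocol 3, Protocol 9.3.2, SAP 1.1.1, SAP section 3, SAP Table 2 and SAP Appendix 6.

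- If exclusion is kept to match the completer estimand, delete loss to follow-up and missing or unevaluable ToC samples from the failure definitions. Say explicitly that a participant who attends ToC without an evaluable culture is outside the primary set.
- If failure is chosen, delete these categories from the exclusion and replacement text, and remove the ToC visit as a condition of entry.

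Report the other rule as a prespecified sensitivity analysis, with the number of participants affected in each arm.

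Under either rule, word Micro-MPP so that participants who took all planned doses and were rescued before ToC stay in the set as failures, with or without a ToC visit. If this departs from the stopping count in Protocol 1.1, which requires a ToC visit, say how the two relate.

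The cost is wording changes in both documents and one extra table. The rate reported under the failure rule may be slightly lower.
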